**DCR protocol is detailed in the annex**

**IF protocol is detailed in the annex**

**Setting of the study:** Endocrinology Service of Hospital Universitary Joan XXIII and Clinical Trial Unit of the IISPV.

A call for participation to the study will be performed at the local media and social networks, according to the recommendations of the IISPV Ethics Committee (these calls have been already done for previous studies by our group with a good acceptance).

**Inclusion criteria:** a) White men and women between 18 and 65 years of age; b) BMI range between 25 and 40 kg/m^2; c) Absence of underlying pathology in medical and physical examination, except for those related to excess weight; d) Signature of the informed consent for participation in the study.

**Exclusion criteria:** a) Serious systemic disease not related to obesity, such as cancer, kidney, or severe liver disease. b) Systemic diseases with intrinsic inflammatory activity (autoimmune diseases such as rheumatoid arthritis and asthma); c) Pregnancy and lactation; d) Vegetarians or subjects subjected to an irregular diet; e) Patients with severe eating disorders; f) Patients with clinical symptoms and signs of infection in the previous month; g) Patients with chronic anti-inflammatory steroid treatments and/or nonsteroidal anti-inflammatory drugs; h) Recent antibiotic treatment; i) Psychiatric history; j) Uncontrolled alcoholism or drug abuse.

##### **Sample size:**

See annex

##### 1A.a- Procedure:

##### **For the IF protocol:**

Subjects will meet a registered dietitian at the beginning of the study and every two weeks to learn how to follow the IF regimen at home. During each counseling session, the dietitian will work with the subject to develop individualized fast day meal plans. These plans will include menus, portion sizes and food lists that can be consistent with their food preferences and prescribed calorie levels for the fast day. During these sessions, subjects will also be instructed as to how to make healthy food choices on the ad libitum food intake days.

##### **For the DCR protocol:**

Subjects will meet a registered dietitian at the beginning of the study and every two weeks to learn how to prepare and follow an adequate caloric restriction diet. During each counseling session, the dietitian will work with the subject to develop individualized meal plans. These plans will include menus, portion sizes, and food lists that are consistent with their food preferences and prescribed calorie levels for the rest of the week.

##### 1A.b-Adherence to the IF diet:

Subjects will be asked to report any extra food item consumed on the fast day that did not comply with their prescribed plan by using the extra food record (*efr*). The *efr* will be reviewed by the study dietitian at each visit. If the *efr* indicates that the subject ate an extra food item on a fast day, that day will be labelled as "not adherent". If

## HEALTH RESEARCH PROJECTS

the *efr* reveals that the subject did not eat any extra food item, that day will be labelled as "adherent". Adherence data will be assessed each week as 1) total adherence (number of days adherent with diet) and 2) percentage adherence calculated by applying the following formula:

% Adherence = no. fast days adherent/ no. fast days in week x 100.

### 1A.c-Clinical/anthropometrical and analytical variables:

Routine clinical and analytical evaluation: (blood count, routine biochemistry, family and personal history, anthropometric measurements (weight, height, waist and hip circumference), frequency of food (previous week) questionnaires, and chronic treatments if any. The evaluation of physical activity and quality of life will be recorded according to validated questionnaires.

### 1B.-Analytical and functional test variables:

The degree of insulin resistance will be calculated according to the formula: HOMA-IR: [glucose (mmol / L) x insulin (mU / L)] / 22.5. Serum and plasma aliquots will be collected before and after each period of dietary intervention (for analytical determinations), and also stool samples for the study of microbiota.

### 1B.a-Metabolites and circulating factors:

Circulating succinate levels will be determined with EnzyChrom™ Succinate Assay Kit (BioAssay Systems, USA). Serum short chain fatty acids (SCFAs) including acetic (C2), propionic (C3), butyric (C4) and formic acids will be analyzed by chromatography-mass spectrometry according to the methodology published by Lotti C et al [5]; Medium chain fatty acids (MCFAs) will also be quantified by chromatography in a separate run. Serum primary and secondary biliary acids (BA) will be quantified by the liquid chromatography -tandem mass spectrometry (LC/MS/ MS) method on the Ciberdem Metabolomics Platform [http://www.iispv.cat/support\\_plataform/metabolomica.html](http://www.iispv.cat/support_plataform/metabolomica.html).

### 1B.b-Meal Test and study of gastrointestinal hormones:

Before and after each restriction diet (DCR and IF diet) at the beginning and at the end of each period (4 test). 200ml administration of Isosource Energy (Novartis, Switzerland) containing 398kcal (50% carbohydrates, 15% proteins and 35% lipids). Extraction at 0, 15, 30, 60 and 120 minutes. Determination of Plasma concentrations of glucose, insulin, GLP-1 and using the Elisa kit (EZGLP1T-36K EMD Millipore, ThermoFisher) and succinate (EnzyChrom™ Succinate Assay Kit (BioAssay Systems, USA)

### 1C-Microbial composition/metagenomic analysis:

Fresh stools will be collected before and after dietary intervention, which will be immediately frozen and stored at -80°C until they are processed. Three days before sample collection, all patients will be placed on the same diet. They will be asked to complete a questionnaire. The microbial composition will be processed by Illumina Sequencing[6-9]. Briefly, we will obtain the microbial genomic DNA and the total RNA extraction; the sequencing of 16S rDNA and 16S rRNA; metagenomic sequencing; purification, amplification, and sequencing of mRNA; metagenomic and metatranscriptomics analysis [10]; protein extraction, separations and identification and data processing. All the sequences will be deposited in "the European Bioinformatics Institute database", with an access number. Metagenomic analysis will be done in collaboration with the team of [name] from the Institute of Integrative Systems Biology at the Universitat de Valencia, with whom we actively collaborate.

### **Statistical analysis, Study limitations and contingency plan and References:**

See annex

Application No.:  
PI20/00338

HEALTH RESEARCH PROJECT APPLICATION FORM  
STRATEGIC FRAMEWORK

(Please only use the space provided below)

1. Project's capacity of approaching the objectives and priorities of the Societal Challenge of Health, Demographic Change and Well-being of the Spanish Strategy for Science, Technology and Innovation.
2. Relevance of the proposal for clinical-translational research.

1. This project is part of the research oriented towards the challenges of society, whose goal is to improve the citizens' health encompassing the investigation of the most prevalent diseases. Specifically, the proposal focuses on two pathologies that are highly prevalent in the Spanish population: obesity and T2D. Both pathologies are in a phase of progressive increase of epidemic characteristics, (Prevalence of diabetes mellitus and impaired glucose regulation in Spain: the [contact] Study. Diabetologia. 2012 Jan; 55 (1): 88-93 and Incidence of diabetes mellitus in Spain: results of the nation-wide cohort [contact] study. Scientific Reports. 2020 in press). Furthermore, the proposed research combines clinical aspects with biological process research related to the mechanisms involved in obesity and type 2 diabetes.

In this sense, the proposal submitted to this call may allow obtaining useful information in the field of Biotechnology with transfer capacity to clinical setting. Another relevant aspect outlined in the priorities of the Health challenge, is the development of personalized medicine, a relevant challenge that will result in benefits both for the patient, essentially, and for the national health system itself, optimizing therapies and individualizing the best treatment options in each case. Thus, the identification of predictive patterns of differential behavior of patients with T2D under metabolic surgery may help to simplify the choice of the surgical approach, according to a more consistent algorithm than the ones used so far. Previous data from our group, published in first line international journals, supports the validity of our hypothesis in this sense. Furthermore, the study in non-morbid obese patients helps us to cover a wide number of patients who usually ask clinicians for a good, efficacious, and safe dietary regimen to be healthier and feel better. The approach submitted will give us new clues about the efficacy of two common dietary protocols analysing new players in the weight loss mechanisms.

**HEALTH RESEARCH PROJECT APPLICATION FORM  
AVAILABLE RESOURCES**

(Please only use the space provided below)

**Application No.:**  
PI20/00338

**HEALTH RESEARCH PROJECT APPLICATION FORM  
ANNEXES**

**ANNEXES (TEXT)**

Max. 3 pages (15,700 characters)

**The DCR protocol** will be a daily reduction of 500 - 1000 kcal according to each individual's resting metabolic rate [1]; with a nutrient composition: < 30% of calories from fat, 15 - 25% from protein, 45 - 50% from carbohydrates [2].

**The IF protocol** will involve fasting for two days (non-consecutive) out of seven, with the fasting days separated by at least one day. A fasting day would entail the consumption of ~ 400-600 kcal at the evening meal (between 12,00 and 15,00 hours to ensure that each subject was undergoing the same duration of fasting), but no other caloric intake, and the participants can consume their desired intake on the other five days. The nutrient composition of the prescribed fasting day meal will be approximately: Total Fat: 13 g (60% mono or polyunsaturated fat), Protein 25g, Carbohydrate 60 g and Fiber 10 g. During fasting days, participants may consume water, tea or coffee (may contain milk max 10cc or cream, max 5 cc), unsweetened beverages such as iced coffee or tea, or a clear soup of vegetable broth.

**Sample Size:**

We have considered this trial as a pilot study. In this sense and following the recommendations on the calculation of the sample size for pilot studies [3], we have considered that a sample of at least 15 subjects per subproject (considering a dropout of 20% during follow up) will be sufficient to obtain valid exploratory data that allow us, in future, to carry out larger epidemiological studies [4].

**Statistical analysis:**

Strategy of the main statistical analysis: The data will be shown as percentages (categorical variables), means +/- standard deviation (continuous variables with normal distribution) or median with interquartile range (continuous variables with

non-normal distribution). The normality of the variables will be analysed with the Kolmogorov-Smirnoff test. To perform the Comparisons of each pre and post intervention group test for paired data will be used. To compare variables The McNemar test (paired data) will be used categorically / qualitatively. The continuous variables of normal distribution will be analysed with the Student t-test for paired data. For continuous variables that do not follow a normal distribution, first we will try to normalize by means of their logarithmic transformation to use parametric tests; if not, non-parametric tests for paired data (Wilcoxon T) will be used. The increase in concentrations of GLP-1 and succinate in response to dynamic functional tests will be measured by calculating the area under the curve. The correlations between the variables will be analysed with the Pearson or Spearman correlation coefficients, when appropriate. Multivariate analysis will be used to predict the clinical and/or functional variables that determine the improvement of clinical and metabolic variables after each diet protocol. Possible confusing variables or effect modifiers (interaction) will be selected based on clinical criteria (data from previous literature) and in function of the result of the univariate analysis ( $p < 0.20$ ). All calculations will be performed with the STATA software package (v13.1 for Mac; StataCorp LP, College Station, Texas) and a value of bilateral  $p < 0.05$  will be used as significant.

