### *Specific proposal subproject 1:*

#### Weight loss

**Daily calorie restriction diets (DCR)** and more recently, diets that incorporate **intermittent fasting (IF)**, are suitable methods that can reduce obesity and its associated comorbidities including T2D [30]. Both (DCR and IF), have shown **similar efficacy** in improving body composition, reducing cardiovascular risk factors, improving glycemic control, insulin sensitivity and insulin secretion. The **benefits of hypocaloric diets** are dependent on **weight loss capacity and on the degree of fat mass reduction**. However, diets involving **IF**, particularly those adapted to the individual's **circadian rhythm (eTRF early-time-restricted-feeding)**, can achieve similar **benefits even without weight loss** [31,32].

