#### Specific objectives of Subproject 1 (SP1)

1a. - To investigate whether IF is better than DCR in terms of metabolic improvement through the study of:

- 1) the dynamics of gastrointestinal hormones and energy sensing metabolites
- 2) the intestinal microbiome
- 3) variability on succinate and SCFAs MCFAs and BA after weight loss

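### The analysis plan names only pre-versus-post paired comparisons and never specifies the IF-versus-DCR contrast that objective 1a asks for

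*Combined protocol and SAP*

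**What the plan says.** The objective is comparative. Under Specific objectives of Subproject 1, 1a reads "To investigate whether IF is better than DCR in terms of metabolic improvement through the study of" gastrointestinal hormones and energy-sensing metabolites, the microbiome, and variability in succinate, SCFAs, MCFAs and bile acids. Section 1A (Design) describes a randomised cross-over with n = 15, two 8-week periods and a 4-week washout.

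The Methodology section sends all statistics to the annex. There, under Statistical analysis, the only comparison named is "To perform the Comparisons of each pre and post intervention group test for paired data will be used". The tests listed are McNemar, the paired t-test and, where log transformation fails, the Wilcoxon paired test. The rest covers descriptive summaries, a normality check, areas under the curve, correlations, and a multivariate search for variables "that determine the improvement of clinical and metabolic variables after each diet protocol". No sentence names a contrast between the diets, an estimate or interval for it, or a term for diet, period or sequence.

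The data for such a contrast are planned. Section 1B states "Serum and plasma aliquots will be collected before and after each period of dietary intervention", and section 1B.b schedules a meal test at the start and end of each of the two periods, four per participant.

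**The concern.** Carried out as written, the plan gives two results, one for each diet's change from its own baseline. Neither result, nor the pair set side by side, tests whether the changes differ. Each pre/post change also contains whatever is common to both periods: time, the attention of being in a study, and regression to the mean. A randomised within-person comparison exists to remove these, so the written analysis gives up the main advantage of the design.

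A finding that both diets improved would leave objective 1a unanswered. The background (Weight loss) makes that plausible for the classical outcomes, since it reports comparable efficacy of the two diets "in improving body composition, reducing cardiovascular risk factors, improving glycemic control, insulin sensitivity and insulin secretion".

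The Sample Size annex says the sample "will be sufficient to obtain valid exploratory data that allow us, in future, to carry out larger epidemiological studies". A larger IF-versus-DCR trial would need the within-person SD of the difference between diets. It can be calculated from the planned data, but it is not a planned output.

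**Working it through.** **The plan's own figure.** The 15 participants rest on a pilot-study recommendation, with no effect size, SD or power, so 15 cannot be reproduced as a power calculation. With the stated 20% dropout, 15 × (1 − 0.20) = 12 completers. The text can also be read as 15 completers, so both are shown.

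**Inputs.** From the documents: two-sided 0.05; n = 12 or 15; paired tests. Assumed: normal changes, in units of the SD of change, and a correlation ρ of 0, 0.3 or 0.5 between a participant's two changes. Each setting was simulated with 40,000 trials.

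**Equal true effects.** Suppose the better diet were read off from which within-diet test is significant. The plan does not state this rule, but it leaves room for it. The share of trials with exactly one diet significant, over the range of ρ, is:

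| True change in both diets | n = 12 | n = 15 |
|---|---|---|
| 0.3 SD | 20–27% | 23–31% |
| 0.5, 0.7, 0.9 SD | 23–48% | 14–49% |
| 1.2 SD | 6–7% | about 2% |
| 1.5 SD | under 1% | under 1% |

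A direct paired IF-versus-DCR test rejects in 4.8–5.3% of trials in the same settings.

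*Check at ρ = 0.* If each within-diet test has power p, the share is 2p(1 − p). Noncentral-t power at n = 12 is 0.353, 0.599 and 0.810 for 0.5, 0.7 and 0.9 SD, which gives:
- 2 × 0.353 × 0.647 = 0.457
- 2 × 0.599 × 0.401 = 0.480
- 2 × 0.810 × 0.190 = 0.308

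These match the simulation. The peak lies between the grid points: at 0.6 SD, p = 0.475 and 2 × 0.475 × 0.525 = 0.499, or about 50%.

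**Unequal true effects.** With large effects the failure is the opposite one. Take true changes of 1.2 and 2.0 SD, a difference of 0.8 SD. Both within-diet tests are significant in about 96% (n = 12) and 99% (n = 15) of trials, so they do not separate the diets. The direct contrast detects the difference in 43–71% and 53–82%. As a check, the standardised difference at ρ = 0.5 is 0.8/√(2(1 − 0.5)) = 0.8, for which noncentral-t power is 0.714 (n = 12) and 0.821 (n = 15).

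**Precision available.** The 95% CI half-width for IF minus DCR, in SD of change, is t(0.975, n − 1) × √(2(1 − ρ)/n):
- n = 12: 0.90 (ρ = 0) to 0.64 (ρ = 0.5)
- n = 15: 0.78 to 0.55

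Adjusting for period takes one more degree of freedom. With near-equal sequence groups the ranges become 0.64–0.91 and 0.56–0.79.

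**The case against.** The strongest reply is that the plan is under-specified, not wrong. The sentences on the paired t-test and Wilcoxon test do not say what is paired, and a paired test is the ordinary simple between-diet analysis in a cross-over. The listed tools could therefore answer objective 1a. That is true, but it is the reader's inference. The one pairing the plan names is pre with post, and a plain paired test would still leave period unaddressed.

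The percentages for one significant diet depend on a decision rule that the plan does not state and on assumed effects and correlations. At a correlation of 0.8 they fall to 13–21% (n = 12) and 9–22% (n = 15) across 0.3–0.9 SD. This stands: they illustrate a risk and are not a forecast. The gap itself does not depend on them.

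The background's statement of comparable efficacy concerns classical metabolic outcomes. For gut hormones, energy sensors and the microbiome, the section on health benefits of intermittent fasting says in-depth work is lacking. This also stands. That both diets improve is therefore plausible context, not an established expectation for every outcome under 1a.

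Finally, this is a declared pilot in a length-limited grant form. That excuses the lack of a power calculation. It does not excuse leaving out the contrast that the trial's own objective asks for, in a text that goes as far as naming the software and the significance level.

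**Conclusion.** The concern holds and should be dealt with before analysis. The statistical annex specifies no between-diet comparison, and no other section supplies one, so the plan as written cannot answer objective 1a. This conclusion comes from reading the text and needs no assumed number.

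The numerical consequences are conditional. With equal effects of 0.3 to 0.9 SD and a correlation of 0 to 0.5, separate tests would split the diets in roughly 14–50% of trials, depending on effect, correlation and n. The split is rare at 1.2 SD and above, where both tests tend to be significant and do not separate the diets. The defect lies in the written analysis, not in the data collection.

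**What to change.** State the within-person IF-minus-DCR contrast, accounting for period, as the main comparison for objective 1a, and say which outcomes it applies to. For each, report the estimate, its 95% CI and the within-person SD of the difference. Either of two analyses will serve:

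- the paired difference of the two period changes (IF change minus DCR change), adjusted for sequence, which removes a period effect; or
- a mixed model with diet, period and period baseline as fixed effects and a random participant effect, which also keeps participants who complete only one period.

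The two treat baseline differently, so choose one before the data are analysed. Keep the within-diet pre/post tests as descriptive. Given the pilot status, no powered superiority test is needed.

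The cost is a few sentences in the SAP and a few lines of Stata code. No new data, visits or participants are needed, because pre and post measurements in both periods are already planned.

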### *Effect of weight loss on succinate levels:*

In addition to intake and dysmetabolic situations, **circulating levels** are also likely to undergo **changes** after weight loss. Severely obese patients, with and without dysglycemia, are able to reverse high circulating levels **after weight loss** [26]. In these patients, decreased circulating levels are paralleled with a restoration of the "**physiological**" response after food ingestion observed in non-obese subjects (*Submitted in Diabetes Care, figure 2*). Interestingly, this behavior is **highly like** what we observe with **incretin hormones** after a meal ingestion. This supports the conceptual hypothesis that succinate is a good marker of metabolic health, which can be especially useful as a **biomarker** in certain circumstances as we have already noted in the case of **diabetes remission** following metabolic surgery [26].

In summary, among the mechanisms involved in weight control, energy sensing metabolites are opening new paths to help better understand the concept of metabolic flexibility and propose new therapeutic approaches in diseases such as obesity and diabetes. In this field, typically intracellular energy metabolites such as succinate are now being considered relevant in their extracellular signalling function through their specific receptor in metabolically sensitive

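### Does the plan need to say whether the meal-test area under the curve is total or incremental?

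*Combined protocol and SAP*

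**What the plan says.** The Annex, under Statistical analysis, defines the meal response in one sentence: "The increase in concentrations of GLP-1 and succinate in response to dynamic functional tests will be measured by calculating the area under the curve". It gives no integration rule, no treatment of the time-0 value and no rule for dips below baseline. The same section adds that "The correlations between the variables will be analysed with the Pearson or Spearman correlation coefficients", without naming any pair.

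Section 1B.b sets the meal-test samples at 0, 15, 30, 60 and 120 minutes, with a test at the start and end of each diet period. Section 1B states that "Serum and plasma aliquots will be collected before and after each period of dietary intervention", and section 1B.a begins "Circulating succinate levels will be determined with" and names the assay kit. Neither says whether the resting succinate value comes from the meal-test time-0 tube or from another sample.

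The objective is "To investigate whether IF is better than DCR in terms of metabolic improvement", studied through, among other things, "the dynamics of gastrointestinal hormones and energy sensing metabolites" and "variability on succinate and SCFAs MCFAs and BA after weight loss". The background section on weight loss reports that, in severely obese patients, "decreased circulating levels are paralleled with a restoration of the" normal response to food.

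**The concern.** Both the resting level of succinate and its meal response are study variables, and total area mixes the two. If intermittent fasting (IF) and daily caloric restriction (DCR) lowered fasting succinate by different amounts, a comparison on total area could show a diet difference in meal response where none exists, or hide a real one.

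Incremental area avoids this but subtracts the time-0 value across the whole curve. Any error in that one sample then enters the area with a large negative weight. If the same sample also supplies the fasting value, the two share error with opposite signs. A negative correlation could then appear by itself, in the direction the background leads the reader to expect: lower succinate, better response. A measurement artefact might be reported as support for the hypothesis.

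**Working it through.** The plan gives no area or correlation figure to reproduce. The sampling times come from section 1B.b. The sample size of 12 is 15 × (1 − 0.20), reading the Annex's 15 as already inflated for 20% dropout. The trapezoidal rule and all levels and standard deviations (SDs) are assumptions.

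**Weights.** The trapezoidal weights at 0/15/30/60/120 minutes are 7.5, 15, 22.5, 45 and 30, which sum to 120. Subtracting the time-0 value over 120 minutes changes its weight to 7.5 − 120 = −112.5. With equal independent error at each time point, the error SD is multiplied by √(7.5² + 15² + 22.5² + 45² + 30²) = 60.9 for total area and by √(112.5² + 15² + 22.5² + 45² + 30²) = 127.7 for incremental area, a ratio of 2.1.

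**Diet comparison.** In total area, a between-diet difference d in fasting fall contributes −120d. For an increment profile of (0, 0.25, 0.5, 1, x) times the peak, with x = 0, 0.25 or 0.5, the area per unit of peak is 60, 67.5 or 75. Each extra unit of fasting fall therefore looks like a loss of 120/75 = 1.6 to 120/60 = 2.0 units of peak. In incremental area the fasting level cancels.

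**Correlation.** Let v be the variance of the true fasting level between visits, a the assay error variance, and p the variance of the peak, with x = 0.25 and response independent of fasting level. For changes between two visits a common factor of 2 cancels, and:

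- incremental: r = −112.5a / √[(v + a)(67.5²p + 16312.5a)]
- total: r = (120v + 7.5a) / √[(v + a)(120²v + 67.5²p + 3712.5a)]

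Here 16312.5 and 3712.5 are the squares of 127.7 and 60.9 before rounding. With visit SD 8, assay SD 5 and peak SD 8 (v = 64, a = 25, p = 64):

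- incremental: −2812.5 / √(89 × 699412.5) = −0.36
- total: 7867.5 / √(89 × 1306012.5) = +0.73

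**Simulation.** There were 20,000 replicates with n = 12, fasting level 100, between-subject SD 25, peak rising from 10 to 30, and fasting and peak changes independent. False correlation means p < 0.05 for change in the time-0 value against change in the area. The false diet difference is for total area at a fasting-fall difference of 0/5/10 units with equal meal gains. Power is for a true 20-unit difference in peak gain with equal fasting falls.

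| Visit SD, assay SD | Incremental: r, false correlation | Total: r, false correlation | False diet difference, total | Power, incremental / total |
|---|---|---|---|---|
| 8, 5 | −0.36, 21% | +0.73, 83% | 5/13/39% | 73% / 46% |
| 5, 10 | −0.73, 82% | +0.33, 19% | 5/15/47% | 34% / 56% |
| 8, 10 | −0.63, 65% | +0.52, 43% | 5/12/32% | 34% / 40% |
| 8, 15 | −0.75, 86% | +0.39, 24% | 5/10/26% | 18% / 33% |
| 15, 5 | −0.21, 10% | +0.90, 100% | 5/8/17% | 72% / 20% |

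Incremental area gives a false diet difference in 5% of trials throughout. Against a fasting value with independent assay error, its false correlation rate is also 5% in every row.

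**Smaller error.** With visit SD 8, an assay SD of 3 gives r = −0.18 and 8% significant; an assay SD of 2 gives r = −0.09 and 6%. With no error in the time-0 sample the incremental coupling is zero.

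**The case for a change.** The case for a change is that the meal response carries one of the stated objectives, yet its measure is undefined. The two readings push a correlation with fasting level in opposite directions, and settling the definition beforehand would stop the choice being made after the data are seen. The Annex also selects confounders and effect modifiers at univariate p < 0.20. At that threshold the incremental area and its own time-0 value would be flagged in 31% to 96% of simulated trials instead of 20%, if that pair were screened. A clarifying sentence costs almost nothing.

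Part of this stands. The definition is missing, and zero is not the right null value if anyone correlates an area with the time-0 sample inside it. The rest is weaker:

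- The diet-comparison bias needs the less natural reading of the sentence plus a between-diet difference in fasting succinate change that no section predicts.
- The correlation artefact needs a pair the plan does not name, a shared sample the plan does not specify, material error, and a substantive reading of the result.
- Fixing one measure is not a clear gain. Incremental area doubles the weight of assay error, and total area is the more powerful in three of the five settings.
- Using a separate aliquot is not a full cure. If it comes from the same draw, draw-level variation is still shared. Adding an assumed draw-level SD of 5 to the first setting still gives r = −0.25 and 12% significant.

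**Conclusion.** No change to the plan is needed. The omission is real but is the kind of detail an analyst settles in the obvious way: a rise in response to a test meal is measured above its starting value. On that reading the fasting level drops out and the diet comparison stays at 5%. If total area were used, a 10-unit difference in fasting fall on an assumed level of 100 would give a false diet difference in 17% to 47% of trials, but equal falls give 5%.

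The correlation problem is a caution for interpretation. It is not a defect in a planned analysis. For incremental area the coupling is not inevitable: it vanishes without error in the time-0 value, or when the fasting value has independent error. For total area the correlation is positive whenever response and resting level are unrelated. The documents give neither assay precision nor visit-to-visit variation, so the simulated rates are illustrations and not a range for this trial.

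The choice between the areas is a fair trade-off, and all five time points are retained, so nothing is lost by leaving the sentence as it stands in a study presented as an exploratory pilot.
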